### **1.2** Table of assessments (ToA)

The table of assessments (ToA) is shown below.

Protocol PQR309-009

PIQUR Therapeutics AG - Confidential

Version 5.0 Amendment date: see date of last approval

# Table 2:Table of Assessments (ToA)

	Screening	ning			On T	On Treatment Visits	/isits					
	Day -28 to -1	Day -1	Day 1	Day 8	Day 15	Day 22	Day 43	Day 64	Day 85	week 18 and subsequently every 6 weeks	End of Treatment	End of Study 
Visit	01	02	03	04	05	90	07	08	60	10 - n	within 7 days of	30 davs after last
Visit Window		none	əuou	none			/+	+/- 3 days				dose (+/- 3 days)
ASSESSMENT												
Signed ICF	x											
Confirm NOTCH1 LOF mutation	×											
Medical history, other known mutations, previous and	^											
ongoing metucations, termographics Cofinine test (urine based)	< ×			at the	e discretion	of the inve	stigator (on	h for natie	nts with a s	at the discretion of the investigator (only for nations with a smoking history)		Τ
Vital Signs	;	Х	X	X	X	X	X	X	X	X	X	
Height	х											
Weight		Х		х	Х	Х	Х	Х	Х	Х	Х	
Physical Examination	х										Х	
ECOG performance status		$X^3$			Х	Х	Х	Х	Х	Х	Х	
Patient-reported questionnaires (GAD-7 and PHQ-9)	Х			Х	Х	Х	Х	Х	Х	Х	Х	
Hematology	Х		Х	Х		Х	Х	Х	Х	Х	Х	
Full Blood chemistry	Х										Х	
Limited Blood chemistry & Fasting Blood Glucose		Х	Х	Х	Х	Х	Х	Х	Х	Х		
HbA1c	Х										Х	
Pregnancy test 	$X^{2a}$						$X^{2b}$	$\mathbf{X}^{2\mathrm{b}}$	$X^{2b}$	$X^{2b}$	${ m X}^{2a}$	
Radiological tumor assessment	x						Х		Х	Х	х	
Bimiralisib oral administration				Ih p	rior to brea	kfast  (fast	Ih prior to breakfast  (fasted) on Day I and 2 of every week	I and 2 of	every week			
Safety ECG	х										Х	
PK sampling 			Х	Х		Х	Х	Х				
ctDNA blood sampling	Х						Х				Х	
Dermatologic evaluation 	Х						Х	Х	Х			
Collection of archival tissue (if available)	Х											
Concomitant Medications						Every visit o	ifter the firs	st dose unti	l 30 days aj	Every visit after the first dose until 30 days after last dose		
Adverse Event monitoring						Every visit c	ufter the firs	st dose unti	l 30 days aj	Every visit after the first dose until 30 days after last dose		
Serious Adverse Event monitoring				Col	ntinuous frc	m signing a	Continuous from signing of ICF until 30 days after last dose	30 days af	ter last dos	0		

Page 16 of 81

Protocol PQR309-009	PIQUR Therapeutics AG - Confidential
Footnotes:	
1: for women of childbearing potential only	
2a: serum HCG	
2b: serum HCG or urine test	
3: ECOG may be collected anytime between day -2 and immedi	nmediately prior to first dose on day 1
4: PK sampling:	
- one pre-dose sample (prior to bimiralisib administration)	
- one post- dose sample within 1 - 3 hours post bimiralisib administration prior to food intake	administration prior to food intake
5: patients following the ranitidine mitigation strategy wil	5: patients following the ranitidine mitigation strategy will take bimiralisib on an empty stomach in the early evening at least 1 hour before dinner
6: can be done via phone call; any bimiralisib-related ong	6: can be done via phone call; any bimiralisib-related ongoing adverse events have to be followed up until resolved to baseline or stabilized
7: Patients will have the option to undergo a standard of ca If actinic keratosis (AK) or keratoacanthomas (KA) are photography will subsequently be repeated every 6 week no further dermatological evaluations on study.	7: Patients will have the option to undergo a standard of care (SOC) skin cancer screening exam by a collaborating, board-certified dermatologist during screening. If actinic keratosis (AK) or keratoacanthomas (KA) are identified, structured skin photography will be performed to map AK or KA lesions. Structured skin photography will subsequently be repeated every 6 weeks to document changes in lesion numbers and size. If no AK or KA lesions are identified, there will be no further dermatological evaluations on study.

Page 17 of 81

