### 4.5.2.9 Neutropenia

There is no MoA or PCS evidence for bimiralisib to induce neutropenia.

It is important to note that most neutropenia cases were reported in a study where patients are concomitantly using eribulin, which is known to induce neutropenia in 80% of treated patients with a similar disease. However, neutropenia and febrile neutropenia events have also been reported in studies 002 and 005.

This supports that there is a causal relationship between bimiralisib and events of neutropenia and febrile neutropenia, and neutropenia is considered an important identified risk. There is no causal relationship between bimiralisib and the occurrence of infection events, including but not limited to sepsis. There is no causal relationship between bimiralisib and any fatal outcomes of infection events related to neutropenia.

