### 7 **IMP administration**

### 7.1 **IMP dosing instructions**

Patients will be treated with 140 mg bimiralisib p.o. once daily on two consecutive days followed by five days without treatment in consecutive 7-day treatment blocks. Patients will follow this iterative "2d on / 5d off" treatment scheme until unacceptable toxicity, tumor progression, patient's request for withdrawal, investigator judgment or death, whichever comes first.

Bimiralisib should be taken in the morning at the same time on an empty stomach at least 1 hour before breakfast with a full glass of non-carbonated, non-flavored water (~7 ounces or 200ml).

For patients who are unable to swallow bimiralisib capsules, capsule content is to be suspended in non-carbonated, non-flavored water. As for oral capsule administration, bimiralisib suspension is to be administered in the morning on an empty stomach. Bimiralisib suspension may be administered by mouth or through a gastric feeding tube as applicable following standard local practice, including rinsing of the tube with water. Feeding tubes that bypass the stomach (e.g. J tubes) cannot be used for bimiralisib administration. In total, suspension and rinsing volume – by tube or by mouth – should be equivalent to about 7 ounces.

*Exception:* patients who follow the ranitidine mitigation strategy will take bimiralisib in the evening on an empty stomach at least 1 hour before dinner. Patients should be instructed not to

bite or chew on the capsules. In case of breakage of the capsules in the oral cavity, additional water should be taken as a rinse.

Re-dosing is not allowed if the patient vomits after bimiralisib intake.

Should a patient miss drug intake at the scheduled time, the planned dose of bimiralisib may be administered within 12h of delay in the following manner: at least 2 hours after the previous meal and 1 hour before the next meal. In case of longer delay the dose is to be omitted and bimiralisib dosing is to be resumed at the next scheduled day.

At specified clinic visits (Table 2), the study drug will be administered in the clinic with dosing appropriately timed relative to blood sampling for bimiralisib pharmacokinetics. On these days the patient comes to the clinic fasted and should refrain from taking food until the collection of the post-dose PK sample.

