# 9 Study assessments and procedures

Planned time points for all study assessments and procedures are provided in the table of assessments (ToA) Table 2.

Screening / Baseline evaluations must be performed within 28 days prior to first administration of bimiralisib.

During the course of the study, test procedures should occur on schedule whenever possible. Screening and baseline assessments should occur within the indicated windows. Assessments scheduled for Day -1, Day 1 and Day 8 should be performed on this day unless specified otherwise. At all subsequent visits, associated assessments that occur +/- 3 days from the scheduled visit date will not constitute protocol deviations. Tumor assessments (except at baseline) may occur within +/- 3 days from the scheduled date.

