# 9.4.4 Clinical safety laboratory assessments

Blood-based clinical laboratory analyses (hematology, blood chemistry, HbA1c and pregnancy test) are to be performed by a certified local laboratory according to the table of assessment (Table 2).

The cotinine test and serum HCG test or urine-based pregnancy tests may be administered by the site.

Test category	Test name
Hematology panel	Haematocrit, hemoglobin, red blood cell (RBC) count, white blood cell (WBC) count with automatic differential count (for neutrophils, lymphocytes, monocytes, eosinophils and basophils), platelets
Full blood chemistry panel	Fasting plasma glucose (FPG), electrolytes (sodium, potassium, calcium), serum creatinine, alanine-aminotransferase (ALT), aspartate- aminotransferase (AST), alkaline phosphatase (AP), total bilirubin, total

Table 5: Laboratory Tests

Test category	Test name
	protein (albumin), lipids (total cholesterol, triglyceride, LDL, HDL), pancreas (amylase), enzymes (LDH, CPK), and CRP
	Total bilirubin: in case of high level of total bilirubin, fractionated (direct and indirect) bilirubin will be collected
Limited blood chemistry panel	Fasting plasma glucose (FPG), serum creatinine, alanine-aminotransferase (ALT), aspartate-aminotransferase (AST), alkaline phosphatase (AP), total bilirubin) and enzymes (CPK)
	Total bilirubin: in case of high level of total bilirubin, fractionated (direct and indirect) bilirubin will be collected
HbA1c	HbA1c (glycated Haemoglobin)
Pregnancy test	Serum HCG or Urine HCG
Smoking test	Cotinine (urine based)

The sponsor / CRO must be provided with a copy of the local laboratory's certification (if applicable), and a tabulation of the normal ranges and units of each parameter collected in the CRF. Any changes regarding normal ranges and units for laboratory values assessed during the study must be reported via an updated tabulation indicating the date of revalidation. The investigator is responsible for reviewing all laboratory reports for patients in the study and evaluating any abnormalities for clinical significance.

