# 9.6 Pharmacokinetics (PK)

Two blood samples for PK analyses will be collected on the following study days:

- Day 1
- Day 8

- Day 22
- Day 43
- Day 64

The first sample will be a *pre-dose* sample, which will be collected prior to bimiralisib administration. The second sample will be collected within 1 - 3 hours post bimiralisib administration prior to food intake.

Procedural details for collection, processing, storing and shipping of samples are provided in a separate manual. Materials for PK sampling will be provided by PIQUR.

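### Day 15 has a chemistry draw but no blood count in Table 2; adding one is a cheap, low-priority improvement to first detection of brief cytopenias

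*Protocol*

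**What the plan says.** Section 9.4.4 of the protocol leaves the timing of laboratory tests to Table 2 (section 1.2). Three rows of that table matter.

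- The limited chemistry row, "Limited Blood chemistry & Fasting Blood Glucose", is marked at Day -1, Days 1, 8, 15, 22, 43, 64 and 85, and from week 18 every 6 weeks.
- The Hematology row is marked at screening, Days 1, 8, 22, 43, 64 and 85, from week 18 every 6 weeks, and at end of treatment. Day -1 and Day 15 are blank.
- The PK row is also blank at Day 15.

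Table 5 in section 9.4.4 lists the limited panel as "Fasting plasma glucose (FPG), serum creatinine, alanine-aminotransferase (ALT), aspartate-aminotransferase (AST), alkaline phosphatase (AP), total bilirubin) and enzymes (CPK". It contains no blood count, and no other section adds one at Day 15.

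On visit timing, Days -1, 1 and 8 are fixed. After that, section 9 says: "At all subsequent visits, associated assessments that occur +/- 3 days from the scheduled visit date will not constitute protocol deviations".

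On risk, section 4.5.2.9 concludes that "neutropenia is considered an important identified risk". It qualifies this by saying that "most neutropenia cases were reported in a study where patients are concomitantly using eribulin", and adds that "neutropenia and febrile neutropenia events have also been reported in studies 002 and 005".

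The SAP repeats the hypotheses and sample size only and does not address laboratory monitoring.

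**The concern.** Day -1 also has chemistry without hematology, but it precedes the first dose. Day 15 is therefore the one on-treatment visit where blood is taken for chemistry and no count is run. The protocol gives no reason for the difference.

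The result is a 14-day stretch early in treatment, Day 8 to Day 22, with no scheduled count. With the visit window it is 11 to 17 days. A cytopenia that begins after Day 8, causes no symptoms and recovers before Day 22 would not be found by the schedule. Two things would follow:

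- The interruption and reduction rules for related haematological events (Table 4 in section 7.2) could not be applied to it.
- It would be absent from the worst post-baseline grade and shift tables of section 10.4.2.3. Those tables are graded from recorded laboratory values, so a value never measured cannot enter them. Change from baseline in hematology is a listed secondary safety endpoint in Table 3.

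The concern is first detection only. Once a clinically relevant abnormality is known, section 9.4.4 already requires repeat testing.

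**Working it through.** **Is the blank cell real?** Table 2 was extracted from PDF, so the column reading needs an independent check. Section 9.6 says "Two blood samples for PK analyses will be collected on the following study days" and lists Days 1, 8, 22, 43 and 64. The PK row in Table 2, read with the same column alignment, gives those same five days with Day 15 blank. The alignment is therefore sound.

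**Inputs from the documents.** Scheduled counts fall on Days 8, 22, 43, 64 and 85. The next two, at week 18 and 6 weeks later, are taken as Days 127 and 169 (85 + 42, then + 42). The gaps between counts are:

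- Days 8-85: 14 + 21 + 21 + 21 = 77 days.
- Days 8-169: 77 + 42 + 42 = 161 days.
- With a Day 15 count, the 14-day gap becomes 7 + 7 and the totals do not change.

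The longer horizon is relevant because section 4.1 keeps the study open until patients have had at least 6 months of treatment or have stopped.

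**Assumptions not in the documents.** An episode lasts d = 3, 5, 7, 10 or 14 days, onset is uniform over the period, and no unscheduled counts are done.

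**Formula.** An episode is found if the next scheduled count falls within d days of onset, so

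detection = sum of min(gap, d) over the gaps ÷ sum of the gaps.

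For d = 7 over Days 8-85: now 7 + 7 + 7 + 7 = 28, and 28/77 = 36.4%. With Day 15: 7 × 5 = 35, and 35/77 = 45.5%. The gain is 7/77 = 9.1 points.

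| d (days) | Days 8-85 now | with Day 15 | gain (points) | Days 8-169 now | with Day 15 | gain (points) |
|---|---|---|---|---|---|---|
| 3 | 12/77 = 15.6% | 15/77 = 19.5% | 3.9 | 18/161 = 11.2% | 21/161 = 13.0% | 1.9 |
| 5 | 20/77 = 26.0% | 25/77 = 32.5% | 6.5 | 30/161 = 18.6% | 35/161 = 21.7% | 3.1 |
| 7 | 28/77 = 36.4% | 35/77 = 45.5% | 9.1 | 42/161 = 26.1% | 49/161 = 30.4% | 4.3 |
| 10 | 40/77 = 51.9% | 44/77 = 57.1% | 5.2 | 60/161 = 37.3% | 64/161 = 39.8% | 2.5 |
| 14 | 56/77 = 72.7% | 56/77 = 72.7% | 0 | 84/161 = 52.2% | 84/161 = 52.2% | 0 |

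**Visit windows.** Hold Day 8 fixed and let Days 15, 22, 43, 64 and 85 each move by up to 3 days, with all 7^5 = 16,807 combinations weighted equally. The mean gain over Days 8-85 for d = 5, 7 and 10 is then 5.8, 6.5 and 4.9 points. The smallest gain is 1.25 points for each (1/80, when the Day 15 and Day 22 visits are one day apart), and the largest are 6.8, 9.5 and 9.5 points. For d = 14 the gain is zero whenever the Day 22 visit falls on or before Day 22. It can reach 3 onset days when that visit slips to Day 25, because the gap is then 17 days and 17 - 14 = 3.

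**Where the gain lies.** All of it comes from onsets between Day 8 and Day 22. Within those 14 days, nominal detection goes from 5/14, 7/14 and 10/14 (36%, 50%, 71%) to 10/14, 14/14 and 14/14 (71%, 100%, 100%) for d = 5, 7 and 10. The later gaps are untouched: a 21-day gap finds 5/21, 7/21 and 10/21 (24%, 33%, 48%), and a 42-day gap finds 5/42, 7/42 and 10/42 (12%, 17%, 24%).

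**The case against.** The strongest reply is that nothing is broken. No section requires a count at Day 15, sampling that thins out over time is a coherent design, and Day 8 to Day 22 is the second-shortest gap in the schedule. If brief cytopenias matter, the 21- and 42-day gaps are worse. This stands, and it limits the point to an improvement. The case for Day 15 is that a visit and a draw already exist there with no count; closing the later gaps would need visits or draws that the schedule does not have.

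The chemistry draw may also have its own reason. Section 4.5.2.8 reports hyperglycemia in almost half of exposed patients, and section 12.6.1 warns of rapid onset and asks for regular glucose monitoring. The protocol does not give this as the reason for the Day 15 pattern, but it is plausible. It explains why chemistry is drawn; it is no reason against a count on the same blood.

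The consequence is limited too. The target is a silent event that recovers unaided. Under Table 4 in section 7.2, a Grade 3 event resolved within 7 days allows resumption at 140 mg. Adverse events are reviewed at every visit, and section 12.1.8 provides for data review at least every 2 months. All this stands, although review cannot show a count that was never taken.

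A reader might infer three stronger claims that the documents do not support:

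- *That patients are dosed on Day 15 in breach of a safety rule.* Table 4 acts on related, graded adverse events and requires no count before a dosing block.
- *That detection roughly doubles.* That holds only for onsets in Days 8-22 and only for some durations; it is not the effect over the treatment period.
- *That a known share of neutropenias is being missed.* The protocol gives no incidence for bimiralisib alone on this schedule, and section 4.5.2.9 attributes most cases to a study with concomitant eribulin.

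**Conclusion.** The point holds as a cheap, low-priority improvement in safety monitoring. Table 2 schedules chemistry without a blood count at Day 15, and this leaves Day 8 to Day 22 without a scheduled count for a drug whose protocol names neutropenia among its important identified risks.

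On nominal days the gain in scheduled detection is at most 9.1 points over Days 8-85 and 4.3 points over Days 8-169, both for 7-day episodes. It is smaller for shorter and longer episodes and nil at 14 days. These figures rest on assumed durations, uniform onset, no unscheduled counts and, for the longer horizon, a patient who stays on treatment to Day 169. Incidence is unknown, so they cannot be turned into a number of missed events. The response endpoint, the two-stage stopping rule and the sample size are unaffected.

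**What to change.** Mark Hematology at Day 15 in Table 2 and run the count on the blood already drawn there for limited chemistry, before dosing where feasible. The cost is one extra tube and one routine local-laboratory count per patient, plus a one-cell change to the table. No new visit or procedure is needed. If the sponsor prefers to leave the cell blank, a sentence giving the reason would settle the matter.

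The change does not guarantee a result before the Day 15 and Day 16 doses. Section 7.1 says that at specified visits "the study drug will be administered in the clinic with dosing appropriately timed relative to blood sampling for bimiralisib pharmacokinetics", but Day 15 is not a PK day, so in-clinic dosing is not specified there, and no rule holds the dose until a result is available. Nor does the change shorten the later 21- and 42-day gaps.

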### 2 Introduction

### 2.1 Indication: recurrent or metastatic HNSCC

More than 90% of tumors in the head and neck are squamous cell carcinomas (HNSCC) [4, 5]. Often, patients present with advanced disease that is incurable, or requires aggressive treatment, which leaves them functionally disabled. HNSCC is one of the most common cancers worldwide, with incidences of more than 30 per 100'000 population in India, France and Hong Kong. It constitutes about 4% of all cancers in the United States. Diagnosis is confirmed by biopsy of the primary site, and/or fine needle aspiration of any enlarged lymph nodes. A full pan endoscopy allows full assessment of the extent of the tumor and exclusion of tumors at other sites within the head and neck. Imaging is crucial in assessing the site, extent, and relationship of a histologically proved primary tumor, and to detect the presence of enlarged lymph nodes.

Following progression after first line chemotherapy, the standard of care for metastatic or recurrent HNSCC is anti-PD1 immunotherapy based on three pivotal studies. Although patients with higher PD-L1 tumor expression had higher response rates, currently there is no biomarker selection for immunotherapy in HNSCC. In the phase Ib keynote-012 study, patients with metastatic or recurrent HNSCC received pembrolizumab [6]. The overall response rate was 18% and six month PFS was 23%. In the single arm, phase II keynote-055 study patients with metastatic or recurrent HNSCC who were resistant to both platinum and cetuximab received pembrolizumab [7]. The overall response rate was 16% with an additional 19% of patients achieving stable disease. Overall 50% of patients had a reduction in the size of the target lesion. Six month PFS was 23%. In the phase III checkmate 144 study, patients with metastatic or recurrent HNSCC who had progressed after platinum-based chemotherapy were randomized to receive nivolumab or investigator's choice of methotrexate, docetaxel, or cetuximab [8, 9]. One year survival rates were higher in the nivolumab arm (36%) vs. the chemotherapy arm (17%) supporting the approval of nivolumab in this setting. Overall response rates to nivolumab were 13.3% which was higher than that of standard therapy (5.8%).

Although immunotherapy has had a striking effect in some patients with metastatic or recurrent HNSCC, the majority of patients still progress. Standard chemotherapy (methotrexate, docetaxel, others) or cetuximab beyond first line therapy benefits less than 15% of patients.

### 2.2 The PI3K/mTOR pathway

Dysregulation of PI3K/ mTOR signaling and their downstream effectors in cancer have been validated as important steps for the initiation and maintenance of the tumorigenic phenotype. In HNSCC, the PI3K/mTOR pathway is altered in 54% of patients including copy number alterations in *PIK3CA* (35%), *PTEN* (6%), *RICTOR* (7%), *AKT1* (3%), *PIK3R1* (2%), and *mTOR* (3%) [10]. In particular PIK3CA is the third most frequently altered gene (18%) in HNSCC with frequent hotspot mutations in the helical (E542K or E545K) and kinase (H1047R) domains in human papilloma virus (HPV)-negative HNSCC patients and mutations in the helical domain in HPV-positive HNSCC patients [11]. Clinical responses to PI3K/AKT/mTOR

pathway inhibitors have been modest and short-lived in most solid tumors [12, 13] and there are no biomarkers to guide patient selection [13]. Use of PIK3CA mutation as a biomarker is inconclusive, with studies showing both increased sensitivity [14, 15] and no differential response to PI3K/AKT/mTOR inhibitors in clinical trials [16-18]. Clinical responses of PIK3CA mutant tumors to pathway inhibitors are still modest [17, 19]. Consistent with the clinical findings, HNSCC cell lines and patient derived xenografts (PDXs) with PIK3CA mutations were more sensitive to PI3K/mTOR pathway inhibitors than PIK3CAwt HNSCC cells but these drugs led to only cell-cycle arrest with no apoptosis in the mutant cell lines [14, 18, 20].

### 2.3 Bimiralisib

Bimiralisib (PQR309) is best described as a selective pan-Class I PI3K inhibitor with a balanced activity against mTOR. The inhibition of the cellular PI3K/mTOR signaling pathways by bimiralisib translates into potent *in vitro* and *in vivo* anti-proliferative activity with the exception of cell lines expressing mutated *KRAS* [21-25].

Bimiralisib has been studied extensively in non-clinical models *in vivo* and is currently being evaluated in other clinical trials. Further information concerning the non-clinical and clinical properties of bimiralisib can be found in the current oral bimiralisib IB [26].

